
effect on pain self-efficacy is hypothesised to mediate the effects on health outcomes. A secondary objective is to explore if pain self-efficacy mediates the effect of the PainSMART-strategy on health outcomes of interest. The mediation models will be estimated using path-analyses within the framework of Structural Equation Modelling.

Analysis of patient and physiotherapist experience outcomes (PREMs)

The intervention group's scores related to the clarity of the film's key messages will be presented descriptively.

Outcomes relating to the evaluations of the initial physiotherapy consultation will be analysed through descriptive statistics and between group differences for each question. Additional analysis will be conducted for concordance between the patients and physiotherapists ratings on the three paired questions for each group.

Physiotherapists' experiences of their perception of the participating patients' preparedness for the initial consultation will be analysed through descriptive statistics and between group differences.

Analysis of physiotherapist adherence

Data on the physiotherapists' self-reported adherence to the protocol will be cross-referenced with the film, respective control, group consultations each individual physiotherapist has conducted. This, in combination with the film group patients' self-reported exposure to the film, will provide data indicating how many of the participating patients received the full PaintSMART-strategy. This data will enable per-protocol and CACE analyses.

Analysis of qualitative outcomes

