This statistical analysis plan is part of the PainSMART-project which is a collective suite of studies utilising mixed methods. The PainSMART-project was initiated in 2021 with the aim of improving early musculoskeletal pain (MSKP) management through patient-centered MSKP education based on modern pain science. The PainSMART project's motivation is the high burden of MSKP and the issues encountered within primary care clinical practice associated with the persistence of misconceptions surrounding MSKP. The PainSMART-project has to date conducted pilot-studies within the primary care setting that have led to the development of the seven-minute-long digital educational film entitled 'Be PainSMART:er' (hereafter known simply as 'the film'). The film forms the basis for the implementation of a two-stage PainSMART-strategy which consists of exposure to the film prior to the initial physiotherapy consultation and a discussion based on the film between the patient and the physiotherapist at the initial physiotherapy consultation. The aim of this study is to scientifically evaluate the effects of adding the PainSMART-strategy to the current MSKP primary care physiotherapy care pathway in the Swedish healthcare regions of Östergötland (RÖ) and Jönköping (RJL).

Description of specific objectives or hypotheses

The objective of the PainSMART-project is to evaluate the effects of administering the PainSMART-strategy as an adjunct to usual physiotherapy management compared to usual physiotherapy management alone.

Research hypotheses for confirmatory research questions

1. Exposure to the PainSMART-strategy as an adjunct to usual physiotherapy management improves the following outcomes significantly more than usual physiotherapy management alone for patients with MSKP (* = primary outcomes) (H1)

- Reduction in pain intensity*.
- Higher pain self-efficacy*.
- Lower MSKP illness perceptions.
- Higher levels of reassurance of the benign nature of MSKP.
- More adaptive MSKP coping and psychological flexibility.
- Higher self-reported levels of physical activity.
- More positive global ratings of change.
- Lower number of healthcare visits, referrals for diagnostic imaging and to specialist/tertiary care for MSKP, lower analgesic medication use, fewer sick leave days and lower direct costs.

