- More positive and concordant patient and physiotherapist evaluations of MSKP-related shared understanding, communication, participation, involvement and emotional support at the initial physiotherapy consultation.

2. Improvements in MSKP illness perceptions and higher levels of reassurance of the benign nature of MSKP mediate improved pain intensity and pain self-efficacy as a result of exposure to the PainSMART-strategy compared to usual physiotherapy management alone.

The null hypothesis (H0) is that there is no clinically or statistically significant differences between the intervention (film) group and the control group (usual physiotherapy management).

Secondary exploratory research questions

1. What baseline factors are predictive of improved patient outcomes after exposure to the PainSMART-strategy?
2. What baseline factors are predictive of the persistence of MSKP?
3. What type of psychological factors and strategies are associated with patient outcomes after exposure to the PainSMART-strategy?
4. Is pain self-efficacy a potential mediator of the PainSMART-strategy's effect on health outcomes?
5. What are patients and physiotherapists experiences of the PainSMART-strategy?

Study Methods

Trial design

This is a two-armed, parallel group, randomised controlled trial in which the intervention group (PainSMART-strategy + usual physiotherapy management) will be compared to a control group (usual physiotherapy management). Treatment allocation is a 1:1 ratio. The control group and statistician will be blinded. One independent statistician will be blinded for the primary analyses. Another independent statistician will be responsible for database development and linkage of patient and physiotherapist data. The PainSMART-strategy is described in full in the trial protocol.

Randomisation

A computerised randomisation sequence for 800 patients into group A (Intervention group) or B (Control group) has been generated by a blinded statistician using SPSS prior to the start of patient recruitment. Participating patients will be allocated to intervention or control group based on the order of their inception to the study. The randomisation is described in full in the trial protocol.

Framework

The trial's hypotheses apply a superiority testing framework where the PainSMART-strategy is hypothesized to be superior in outcome compared to control.

Determination of Sample size

The sample size calculation is described in full in the trial protocol.

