Data on sick leave days will be collected from the Swedish social security database (Försäkringskassan).

- Time Frame: collected for each participating patient for the time period baseline to three months following completion of data collection for all participants.
- Calculation to derive outcome:
 - Number and proportion of sick leave days from baseline to three months follow-up, as well as between group differences.

Physiotherapist and patient reported experience measure outcomes (PREM)

-Patient reported experiences of the film

The perceived clarity of key messages in the film will be measured via rating the clarity for each message (eight) on a 0-10 NRS by patients in the intervention group. A higher score indicates a clearer message.

- Time Frame: collected directly post first exposure to the film in the intervention group.
- Calculation to derive outcome:
 - Descriptive statistics.

-Patient reported experience of the initial physiotherapy consultation

Patients' experiences of the initial physiotherapy consultation will be measured using seven questions adapted from the National Patient Survey, Sweden. The questions evaluate if the patients felt that they had the possibility to talk sufficiently about their MSKP, whether they felt included in decision making around their care, whether they had the opportunity to discuss any worries and concerns they had regarding their MSKP and to what extent they discussed what they could do themselves to improve their MSKP and health. The patients are also asked if they felt the physiotherapist considered their personal MSKP experiences and explained MSKP in a way that they could understand. The questions are answered on a NRS score range: 0-10, where a higher score reflects a more positive experience in relation to each question.

- Time Frame: collected 24 hours post the initial physiotherapy consultation.
- Calculation to derive outcome:
 - Descriptive statistics and between group differences in each question. Three of the questions will be matched for concordance with the physiotherapists' reported experienced questions.

-Physiotherapist reported experience of the initial physiotherapy consultation

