Patients receive seven questions and physiotherapists 3 questions regarding their experience of the initial physiotherapy consultation. Between group mean difference for responses to these questions will be analysed using independent sample t-tests. These analyses will be presented as mean and SD for each group and the between group difference in mean and CI. Three of the patient questions will be analysed for concordance with the matched physiotherapists' questions. Concordance within the intervention group and control group will primarily be analyzed by calculating intraclass correlation coefficient (ICC) with 95% confidence interval on each question as well as all three questions combined. Two-way random effects model will be used for ICC, assuming raters to be randomly selected. The ratings are single measures analyzed for consistency, to measure systematic differences between ratings. Patients and physiotherapists are treated as two independent raters, rating each of the three questions.

Sensitivity analyses

The following are all re-analyses of the primary and secondary outcomes under different conditions:

- Per-protocol analysis
- Complier average causal effect (CACE) analysis
- Responder analysis
- Complete case analysis (in case of >5% missing data)

Per-protocol analysis

Per-protocol analyses for the primary and secondary outcomes will be conducted to assess robustness of the ITT analyses and to further inform decisions regarding superiority. The sample of the patients for the per-protocol analyses will be as follows:

- Intervention group: patients receiving the PainSMART-strategy with no or minor deviation from protocol.
- Control group: patients receiving intervention with no or minor deviation from protocol.

Data on the physiotherapists' self-reported adherence to the protocol will be cross-referenced with the intervention respective control group patient consultations that each physiotherapist has conducted. This, in combination with the intervention group patients' self-reported exposure to the film, will provide data on deviation from protocol.

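### The planned consistency ICC leaves out the systematic patient–physiotherapist difference it is meant to measure, and no between-arm contrast is named for the concordance part of hypothesis 1

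*SAP*

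**What the plan says.** The SAP section on patient and physiotherapist experience outcome analyses has two parts. Mean scores on each question are compared between arms with independent-samples t-tests. Agreement between the two raters is handled separately: "Concordance within the intervention group and control group will primarily be analyzed by calculating intraclass correlation coefficient (ICC) with 95% confidence interval". One such coefficient is planned per matched item and one for the three items together. The model is two-way random effects with patient and physiotherapist as the two raters, and the type and purpose are given as follows: "The ratings are single measures analyzed for consistency, to measure systematic differences between ratings".

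The claim this has to support is in the SAP's confirmatory hypotheses. Exposure to the strategy "improves the following outcomes significantly more than usual physiotherapy management alone", and the list of outcomes includes: "More positive and concordant patient and physiotherapist evaluations of MSKP-related shared understanding". The Protocol's section on PREM analysis says: "Additional analysis will be conducted for concordance between the patients and physiotherapists ratings on the three paired questions for each group". The SAP outcome definition for the patient questions adds only this: "Three of the questions will be matched for concordance" with the physiotherapists' items.

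**The concern.** Two things do not fit together.

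First, the form of the ICC and its stated purpose contradict each other. An analyst can follow the word consistency or the aim of capturing systematic differences, but not both.

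Second, the hypothesis is comparative and the analysis is not. The t-tests on mean scores address whether evaluations are more positive. For concordance the plan yields four ICCs per arm (three items and one combined) with no contrast, no interval for a difference and no decision rule. If the intervention worked mainly by closing a systematic gap between how patients and physiotherapists rate the consultation, the planned statistic would hardly move. Any claim of greater concordance would then rest on a comparison chosen after the results were seen.

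**Working it through.** The documents give no ICC value, variance or power for concordance, so there is no figure of the plan's own to reproduce. The first result below is algebra. The rest is illustration under stated assumptions.

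**1. The two forms.** Let MSR, MSC and MSE be the mean squares for consultations, raters and error, with k = 2 raters and n pairs.

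- Consistency: (MSR − MSE) / (MSR + MSE)
- Absolute agreement: (MSR − MSE) / (MSR + MSE + 2(MSC − MSE)/n)

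The systematic patient–physiotherapist difference enters only through MSC, which is absent from the first formula. No assumption is needed for this.

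**2. Unbounded scale.** Assume a between-consultation SD of 1.5 (variance 2.25) and a rater error SD of 1 (variance 1). With a constant gap d:

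- Consistency = 2.25/3.25 = 0.69 for every d.
- Agreement = 2.25/(3.25 + d²/2). This is 2.25/3.25 = 0.69 at d = 0, 2.25/3.75 = 0.60 at d = 1, and 2.25/5.25 = 0.43 at d = 2.

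A second set of assumed variances (1.44 and 1.44), in one simulated sample of 204 pairs (408/2, from the Protocol's sample size section), gave a consistency ICC of 0.475 at shifts of 0, 1, 2 and 3 points. The agreement ICC was 0.473, 0.421, 0.290 and 0.188.

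**3. The actual 0-10 scale.** Same SDs as in step 2, physiotherapist mean 7, scores rounded and clipped to 0-10, 600,000 simulated pairs per setting:

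| Gap | Consistency ICC | Agreement ICC |
|---|---|---|
| 0 | 0.67 | 0.67 |
| 1 | 0.66 | 0.58 |
| 2 | 0.62 | 0.39 |

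The consistency ICC moves slightly here, but only because clipping at 10 distorts the scores.

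**4. What a between-arm comparison would see.** One item, 204 pairs per arm, gap 1 in control and 0 in intervention. A contrast of consistency ICCs has power of 7% (one-sided 0.05) or 4% (two-sided 0.05). A contrast of agreement ICCs has 50% or 38%.

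**5. Why the rule has to be named.** Assume a control ICC of 0.50 and 204 per arm, and use Fisher's z with SE 1/√(204 − 1.5) = 0.0703. A direct two-sided 5% test needs a z difference of 1.96 × √2 × 0.0703 = 0.195, that is, an intervention ICC of about 0.63. Requiring the two 95% CIs not to overlap needs 2 × 1.96 × 0.0703 = 0.275, or about 0.68. The same data could therefore support or fail the claim, depending on an unstated rule.

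**6. Which contrast.** The mean absolute paired difference is an obvious candidate, but it shrinks near the top of the scale. With no gap in either arm, moving both raters from mean 7 to 8 or 9 lowers it from 1.08 to 0.99 or 0.81. A test on it was checked with three items, 180 pairs per arm (450 × 0.8 / 2, assuming 80% complete pairs), item error correlation 0.5, and 100 physiotherapists with a leniency SD of 0.5. With no gap in either arm it rejects as follows:

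| Both raters' mean, control to intervention | One-sided 0.05 | Two-sided 0.05 |
|---|---|---|
| 7 to 8 | 38% | 27% |
| 7 to 9 | 98-99% | 97-98% |
| 8 to 9 | 82% | 73% |

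The last row equals its power to detect a true closing of the gap from 1 to 0 (82%/73%). In the same no-gap settings the between-arm difference in the mean signed paired difference held its level, at about 5% one-sided.

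**The case against.** The strongest reply is that little is lost. Each arm's ICC comes with a 95% CI and the arms contain different randomised patients, so an approximate contrast can be worked out from the reported figures. The item means are reported for both raters, so the gap in each arm can be read off. This stands in part: the information is largely there. What is missing is a pre-named contrast and rule, and an interval for the paired difference, which two separate sets of means do not supply. A reader might infer that the arms could not be compared at all; the planned output does not support that.

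A reader might also infer that the item pairing is undefined and the analysis therefore cannot be run. The SAP announces seven patient questions but describes six. After the first four it continues: "The patients are also asked if they felt the physiotherapist considered their personal MSKP experiences and explained MSKP in a way that they could understand". Missing is the item on reaching consensus. However, the Protocol lists all seven, the SAP refers to the Protocol for full outcome definitions, and the physiotherapists have only three questions, whose partners can mostly be recognised by wording. This is editorial.

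A third tempting step is to make the mean absolute paired difference the confirmatory test. The working shows why not. The same hypothesis predicts higher scores in the intervention arm, and higher scores alone can make that test reject.

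Finally, a consistency ICC is a legitimate description of relative agreement. The objection is to the purpose attached to it.

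**Conclusion.** The concern holds, and it is minor. The contradiction within the SAP sentence is a matter of algebra and rests on no assumption. The absence of a named between-arm contrast follows from reading the SAP and Protocol sections side by side.

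The size of the effect does rest on assumptions. The variances, the mean of 7, the completeness of pairs and the 100 physiotherapists are not in the documents, and the Protocol puts the number employed at about 130. Under these assumptions a 2-point gap lowers the agreement ICC from 0.67 to 0.39 and the consistency ICC only from 0.67 to 0.62.

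The scope is one clause on a secondary outcome. Nothing here bears on pain intensity or pain self-efficacy, or on the t-tests of mean experience scores. The test planned for physiotherapists' ratings of patient preparedness is a separate matter.

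**What to change.** In the SAP section on patient and physiotherapist experience outcome analyses:

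1. Specify absolute agreement in place of consistency. Keep the consistency ICC, if wanted, only as a supplement described as relative agreement.
2. For each arm and matched item, report the mean patient-minus-physiotherapist difference with a 95% CI.
3. Add the between-arm difference in that mean signed difference, with a CI that allows for clustering by physiotherapist. Read it as greater concordance only if the intervention arm's gap is closer to zero. If the two gaps have opposite signs the contrast does not settle the question alone, so the per-arm gaps must stand beside it. The alternative is to state that concordance is descriptive and remove it from the confirmatory hypothesis.
4. Do not use the mean absolute paired difference as the decision test. If reported, give it descriptively beside the item means and the share of ratings at 10. Those two summaries also help in reading the signed contrast, because a real gap present in both arms would be compressed near the ceiling too.
5. Editorial: restore the consensus item in the SAP's description of the patient questions and list the three pairs.

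The cost is SAP wording and a few lines of code on data already planned, settled before group labels are opened. Agreement ICCs will be lower than consistency ICCs wherever a gap exists. The signed contrast does not capture random disagreement, which the ICC continues to describe.
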